UNIVERSITY OF THESSALY

SCHOOL OF MEDICINE

**MASTER PROGRAM IN
Methodology of Biomedical research, Biostatistics and clinical
Bioinformatics**

Master Course Thesis

**<< Protocol for a Phase 3, Active (Warfarin) Controlled, Randomized, Double-
Blind, Parallel-Arm Study to Evaluate Efficacy and
Safety of Apixaban In Preventing Stroke and Systemic Embolism in Patients
with Nonvalvular Atrial Fibrillation >>**

[name]

Supervisor: [name]

Evaluator 1: [name]

Evaluator 2: [name]

Larissa, Greece, August 2015

SYNOPSIS

Clinical Protocol

Title of Study: A Phase 3, Active (Warfarin) Controlled, Randomized, Double- Blind, Parallel-Arm Study to Evaluate Efficacy and Safety of Apixaban In Preventing Stroke and Systemic Embolism in Patients with Nonvalvular Atrial Fibrillation

Study Phase: 3

Research Hypothesis: Apixaban is noninferior to warfarin for prevention of stroke (ischemic or hemorrhagic or of unspecified type) or systemic embolism in subjects with atrial fibrillation (AF) and additional risk factor(s) for stroke.

Primary Objective: To determine if apixaban is noninferior to warfarin (INR target range 2.0 - 3.0) in the combined endpoint of stroke (ischemic or hemorrhagic or of unspecified type) and systemic embolism, in subjects with AF and at least one additional risk factor for stroke.

Key Secondary Objectives: To determine, in subjects with AF and at least one additional risk factor for stroke if apixaban is superior to warfarin (INR target range 2.0-3.0) for

- The combined endpoint of stroke (hemorrhagic, ischemic, or of unspecified type) and systemic embolism,
- Major bleeding (ISTH)
- All-cause death.

Study Design: Randomized, double-blind, double-dummy, parallel-arm study assessing apixaban and warfarin with titration based on central monitoring of the international normalized ratio (INR). Subjects will receive active apixaban tablets and placebo warfarin tablets or placebo apixaban tablets and active warfarin tablets.

Screening Period: The protocol includes a screening period of up to 14 days; subjects who meet the inclusion / exclusion criteria are eligible. Subjects with AF and at least one additional risk factors for stroke will be evaluated for study eligibility. Emphasis will be placed on recruiting both warfarin-naïve and warfarin-experienced subjects. Vital signs, a 12 lead electrocardiogram (ECG), and clinical laboratory samples will be obtained during this period.

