2.2 Secondary Objectives

- **Key Secondary Objectives**

The key secondary objectives are to determine, in subjects with AF and at least one additional risk factor for stroke (5.4.1), if apixaban is superior to warfarin (INR target range 2.0 – 3.0) for the combined endpoint of stroke (hemorrhagic, ischemic or of unspecified type) and systemic embolism, major bleeding (ISTH) and all-cause death.

- **Other Secondary Objectives**

To compare, in subjects with AF and at least one additional risk factor for stroke, apixaban and warfarin with respect to the composite endpoint of stroke (ischemic, hemorrhagic, or of unspecified type), systemic embolism and major bleeding, in warfarin naive subjects, the composite endpoint of stroke (ischemic, hemorrhagic or of unspecified type), systemic embolism and major bleeding, the composite endpoint of stroke (ischemic, hemorrhagic or of unspecified type), systemic embolism and all cause death, the composite endpoint of stroke (ischemic, hemorrhagic, or of unspecified type), systemic embolism, major bleeding and all cause death and the composite endpoint of stroke (ischemic, hemorrhagic, or of unspecified type), systemic embolism, myocardial infarction and all cause death.

To assess the safety of apixaban in subjects with AF and at least one additional risk factor for stroke.

UNIT 3 : Ethical Considerations

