8.3.2 Efficacy and Safety Analysis

To begin with, all subjects should be included in the groups to which they will be randomly assigned. This is an "intention to treat" analysis. If the result is statistically significant then will be applied per protocol analysis which should have the same results in intention to treat analysis.

Efficacy Analysis

Primary Censoring Scheme for Efficacy Endpoints

Subjects who do not experience an efficacy endpoint event will be censored at the earlier of their death date (when death is not part of the endpoint), last contact date (for subjects who withdraw consent to be followed up or are lost to follow-up) or the efficacy cut-off date. For endpoints other than all-cause death, the last contact date will be the last date on which the efficacy endpoint can be assessed. For instance, if a subject is only followed for survival status after date X, then date X will be the last contact date in the censoring scheme. For the all-cause death endpoint, the latest date on or prior to the efficacy cut-off date at which survival status can be determined will be used either as the date associated with the endpoint (if the subject died) or the censoring date (if the subject was determined to be alive).

- **Primary Efficacy Analysis**

The primary efficacy endpoint will be the time to first occurrence of confirmed stroke (ischemic, hemorrhagic, or of unspecified type), or systemic embolism during the study, regardless of whether the subject is receiving treatment at the time of the event. The primary objective is to determine if apixaban is non-inferior to warfarin for the primary efficacy endpoint. To conclude non-inferiority it will be necessary to demonstrate that the apixaban event rate for the primary endpoint is not materially higher than the warfarin event rate as measured by the relative risk of apixaban relative to warfarin.

The non-inferiority margin is 1.88 or 1.38 (ie, the margin is the midpoint between 1.0 and 1.88 on a log scale rather than linear scale because the primary parameter estimated is the logarithm of the relative risk)

Tests using each non-inferiority margin will be performed using a Cox proportional hazards model including treatment group as a covariate and stratified by prior warfarin / VKA status (experienced, naïve).

- **Key Secondary Analysis**

For the regulatory claims associated with the primary and the key secondary objectives listed, the following hierarchical testing procedure will be used:

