[name]

26

Non-inferiority for the primary efficacy endpoint will be assessed first. If non-inferiority (using a non-inferiority margin of 1.38) is demonstrated then:

I. superiority for the primary efficacy endpoint will be tested

II. if superiority for the primary efficacy endpoint is

-not demonstrated, then stop

-demonstrated, then non-inferiority for major bleeding will be tested

III. if non-inferiority for major bleeding is

- not demonstrated, then stop

- demonstrated, then superiority for all cause death will be tested.

Safety Analysis

- **Primary Safety Analysis**

The primary safety endpoint will be time to first occurrence of major bleeding during the treatment period. A point estimate and two-sided 95% CI for relative risk and a p-value for the test of equality of rates ($RR = 1$) will be calculated. The test will be performed using a Cox proportional hazards model including treatment group as a covariate and stratified by prior warfarin status (experienced, naïve). Kaplan- Meier methodology will be used to estimate event rates over time. Subjects without events during the treatment period will be censored.

- **Secondary Safety Analysis**

The incidence of confirmed major bleeding events, confirmed clinically relevant non-major bleeding events, minor bleeding events and all bleeding AEs occurring through the end of the treatment period will be summarized by treatment group.

The incidence of AEs and of marked abnormalities in clinical laboratory tests will be summarized by treatment group. All AEs that are serious or that result in discontinuation of study drug will be described in depth

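### The objectives claim superiority on major bleeding, but the testing hierarchy tests non-inferiority for it and the protocol states no bleeding margin

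*Protocol*

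**What the plan says.** **Objectives.** Section 2.2 sets the key secondary objectives as determining "if apixaban is superior to warfarin (INR target range 2.0 – 3.0) for the combined endpoint of stroke". The same sentence goes on to list "systemic embolism, major bleeding (ISTH) and all-cause death". The synopsis gives the same three endpoints as bullets under one stem: "if apixaban is superior to warfarin (INR target range 2.0-3.0) for". Superiority therefore governs all three, major bleeding included.

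**Hierarchy.** Section 8.3.2 (Key Secondary Analysis) states its purpose: "For the regulatory claims associated with the primary and the key secondary objectives listed, the following hierarchical testing procedure will be used". The order is non-inferiority on the primary endpoint at 1.38, then superiority on the primary endpoint. If that succeeds: "demonstrated, then non-inferiority for major bleeding will be tested". If bleeding non-inferiority is shown, superiority on all-cause death follows. The synopsis (Efficacy Analysis) prints the same sequence.

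**Safety analysis.** Separately, the Primary Safety Analysis in Section 8.3.2 gives a relative risk for major bleeding with a two-sided 95% CI and "a p-value for the test of equality of rates". It comes from a Cox model stratified by prior warfarin status. Nothing links this test to the hierarchy.

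**The concern.** The objective and the test meant to support it are different hypotheses. Two of the three key secondary objectives appear in the hierarchy as superiority tests. Bleeding alone appears as non-inferiority. A trial that follows the hierarchy exactly could complete every step and still have no controlled test of the bleeding objective.

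A non-inferiority test also needs a margin, and this protocol gives none for bleeding. The step decides whether all-cause death may be tested at all, so two confirmatory claims depend on it: bleeding directly, and mortality through the gate.

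**Working it through.** **1. Objectives against hierarchy.**

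| Endpoint | Objective (synopsis; 2.2) | Hierarchy (synopsis; 8.3.2) |
|---|---|---|
| Stroke or systemic embolism | superiority | superiority, after non-inferiority at 1.38 |
| Major bleeding (ISTH) | superiority | non-inferiority, no margin |
| All-cause death | superiority | superiority, only if the bleeding step passes |

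Non-inferiority for bleeding is named at steps II and III in both the synopsis and the body, four times in all. It is not an isolated slip.

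**2. Can 1.38 be borrowed?** Section 8.1 starts from the upper confidence limit of 0.53 for warfarin against placebo, inverts it (1/0.53 ≈ 1.88) and takes the midpoint on the log scale. The arithmetic gives √1.88 = 1.371, against the printed 1.38; the difference is immaterial here. The logic is to preserve half of warfarin's benefit on stroke. It says nothing about how much extra bleeding would be acceptable, and the hierarchy attaches 1.38 only to the primary efficacy endpoint.

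**3. How much the undefined margin matters.** The protocol states no bleeding rate, event count or power, so there is no figure to reproduce. I assume D = 400 to 1,000 major bleeds in total. Against the 36,078 patient-years of Section 8.1, that is about 1.1 to 2.8 per 100 patient-years (400/360.78 and 1,000/360.78).

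With 1:1 allocation, SE(log RR) ≈ 2/√D. The step passes at margin M if the upper 95% limit lies below M:

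- largest passing observed RR = M × exp(−1.96 × 2/√D)
- chance of passing = Φ[(ln M − ln RR) × √D/2 − 1.96]

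Example: M = 1.25, true RR = 1, D = 400 gives Φ(0.2231 × 10 − 1.96) = Φ(0.27) = 0.607.

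| Margin | Largest passing observed RR (D = 400 to 1,000) | Chance of passing if true RR = 1 |
|---|---|---|
| 1.0 (superiority) | 0.82 to 0.88 | 2.5% |
| 1.10 | 0.90 to 0.97 | 16 to 33% |
| 1.25 | 1.03 to 1.10 | 61 to 94% |
| 1.38 | 1.13 to 1.22 | 90 to 99.9% |
| 1.50 | 1.23 to 1.33 | 98 to 100% |

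These are chances for the bleeding step once it is reached, taken as independent of the earlier tests. They are not chances that the whole sequence gets that far.

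**4. Cost of a superiority gate.** With true RR = 1 the step passes 2.5% of the time. With a true HR of 0.85 and an assumed 433 bleeds (borrowing the primary event target only for scale), the chance is Φ(0.1625 × 10.40 − 1.96) = Φ(−0.27) ≈ 39%.

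**The case against.** **The analysis plan may hold the margin.** It was not available, and it could fix a bleeding margin before unblinding. This stands. A reader might infer that the step cannot be run at all, but the protocol shows only that it cannot be run from this document. A margin in the analysis plan would still leave a superiority objective paired with a non-inferiority test, since both are fixed in the protocol.

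**The safety test covers superiority.** It does test RR = 1, and such a test outside a hierarchy is ordinary. A reader might infer a family-wise error of about 10% from it. The documents do not support that. The figure of 1 − 0.95² = 9.75% counts errors in both directions of two independent tests; false claims of benefit come to 1 − 0.975² = 4.94%. The protocol also assigns regulatory claims to the hierarchy and nowhere says that it will make one from the safety p-value. The supported consequence is a stated objective with no controlled test, not demonstrated alpha inflation.

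**The mortality test stays protected.** This also stands. In a fixed sequence, all-cause death keeps its type I error control whatever hypothesis precedes it, provided that the bleeding margin is fixed in advance. What is undefined is the condition for reaching the mortality test.

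**The error may lie in the objective.** The documents do not show which text was intended. Both repairs should therefore be open to the sponsor.

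**Conclusion.** The point holds as a contradiction within the protocol, present in both synopsis and body. Superiority on major bleeding is a key secondary objective, yet no step of the sequence said to serve that objective tests it. The step that stands in its place has no stated margin, and the efficacy margin cannot supply one.

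The contradiction itself rests on no assumption. The size does: under equal bleeding rates, the chance that the step opens the mortality test moves from 2.5% to nearly 100% across margins of 1.0 to 1.50, for an assumed 400 to 1,000 bleeds and a normal approximation to log RR. The damage is confined to the third and fourth tests. Both tests on the primary efficacy endpoint come earlier and are untouched.

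**What to change.** Make one of two changes by amendment, before the sponsor sees unblinded data, and make it identically in the synopsis and Section 8.3.2.

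**Option A: match the objectives.** At steps II and III, replace non-inferiority for major bleeding with superiority: RR = 1, two-sided 0.05, using the Cox model already specified for the primary safety analysis. The sequence becomes non-inferiority then superiority on the primary endpoint, superiority on major bleeding, and superiority on all-cause death. It needs no margin and no alpha split. The text change is a few lines. The real cost is the harder gate to all-cause death worked out above, about 2.5% if bleeding rates are equal and about 39% at an HR of 0.85 with 433 bleeds.

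**Option B: keep non-inferiority.** State and justify a bleeding margin on bleeding grounds, add superiority on major bleeding as a separate step with its place relative to all-cause death fixed, and reword the objectives in the synopsis and Section 2.2 to match. This costs a margin justification. If bleeding superiority is placed ahead of all-cause death, the gate is as hard as in Option A; if placed after, mortality is easier to reach and the bleeding superiority claim depends on it.

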Reference Therapy, Dose and Mode of Administration, Duration of Treatment: Oral warfarin dose titrated to a target INR range of 2.0 - 3.0 or matching placebo for the treatment period (average of 2.3 yrs of follow-up from randomization)

Criteria for Evaluation

Primary efficacy endpoint

The primary efficacy endpoint is the time to first occurrence of confirmed stroke (ischemic, hemorrhagic, or of unspecified type) or systemic embolism, regardless of whether the subject is receiving treatment at the time of the event.

Secondary efficacy endpoints

The secondary efficacy endpoints will be time to first occurrence of confirmed:

- ischemic stroke or stroke of unspecified type
- hemorrhagic stroke
- systemic embolism
- all cause death
- composite of stroke (ischemic, hemorrhagic, or of unspecified type), systemic embolism, major bleeding
- composite of stroke (ischemic, hemorrhagic, or of unspecified type), systemic embolism and major bleeding in warfarin naive subjects
- composite of stroke (ischemic, hemorrhagic, or of unspecified type), systemic embolism, all cause death
- composite of stroke (ischemic, hemorrhagic, or of unspecified type), systemic embolism, major bleeding, all cause death
- composite of stroke (ischemic, hemorrhagic, or of unspecified type), systemic embolism, myocardial infarction, all cause death.

Primary safety endpoint

The primary safety endpoint will be time to first occurrence of confirmed major bleeding during the treatment period.

Secondary safety endpoint

The secondary safety outcome for this trial is a composite of confirmed major bleeding and confirmed clinically relevant non-major bleeding. Other safety outcome measures will also be assessed, and will include minor bleeds, fractures and other AEs as well as abnormal standard clinical laboratory test results.

Bleedings

Major bleeding is defined as bleeding that is clinically overt and that satisfies one of the following criteria 1) bleeding resulting in a decrease in hemoglobin of 2 g/dL or more over a 24-hour period; 2) bleeding leading to a transfusion of 2 or more units of packed red blood cells; 3) bleeding that occurs in a critical site (intracranial, intraspinal, intraocular, pericardial, intra-articular, intramuscular with compartment syndrome or retroperitoneal); or 4) bleeding that leads to death.

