Efficacy Analysis: The primary efficacy endpoint will be the time to first occurrence of confirmed stroke (ischemic, hemorrhagic, or of unspecified type), or systemic embolism during the study, regardless of whether the subject is receiving treatment at the time of the event. The primary objective is to determine if apixaban is non-inferior to warfarin for the primary efficacy endpoint. To conclude non-inferiority it will be necessary to demonstrate that the apixaban event rate for the primary endpoint is not materially higher than the warfarin event rate as measured by the relative risk of apixaban relative to warfarin. Tests using each non-inferiority margin will be performed using a Cox proportional hazards model including treatment group as a covariate and stratified by prior warfarin / VKA status (experienced, naïve). For the regulatory claims associated with the primary and the key secondary objectives listed, the following hierarchical testing procedure will be used:

Non-inferiority for the primary efficacy endpoint will be assessed first. If non-inferiority (using a non-inferiority margin of 1.38) is demonstrated then:

I. superiority for the primary efficacy endpoint will be tested

II. if superiority for the primary efficacy endpoint is

-not demonstrated, then stop

-demonstrated, then non-inferiority for major bleeding will be tested

III. if non-inferiority for major bleeding is

- not demonstrated, then stop

- demonstrated, then superiority for all cause death will be tested.

Safety Analysis: The primary safety endpoint will be time to first occurrence of major bleeding during the treatment period. A point estimate and two-sided 95% CI for relative risk and a p-value for the test of equality of rates ($RR = 1$) will be calculated. The test will be performed using a Cox proportional hazards model including treatment group as a covariate and stratified by prior warfarin status (experienced, naïve). Kaplan- Meier methodology will be used to estimate event rates over time. Subjects without events during the treatment period will be censored. The incidence of confirmed major bleeding events, confirmed clinically relevant non-major bleeding events, minor bleeding events and all bleeding AEs occurring through the end of the treatment period will be summarized by treatment group.

TABLE OF CONTENTS

FRONT COVER.....	1
SYNOPSIS.....	2
TABLE OF CONTENTS.....	7
1 INTRODUCTION.....	9
1.1 Atrial Fibrillation.....	9

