At the INR visits, only INR monitoring with POC device, assessment of outcomes, and assessment of study medication compliance will be performed. In addition, at the quarterly visits during the treatment period (Months 3, 6, 9, 15, 18, 21, 27, 30, 33, 39, 42, 45, 51, 54, 57) assessment of changes in concomitant medication, vital signs and laboratory assessments will be performed and at the yearly visits during the treatment period (Months 12, 24, 36, and 48) physical measurements and a 12 lead ECG will be obtained, and electrocardiograms will be performed. All subjects will be followed for the development of stroke (hemorrhagic, ischemic or unspecified), systemic embolism, myocardial infarction, death, bleeding, hospitalization or treatment discontinuation until the end of the study. Follow-up of subjects who discontinued study drug prior to the attainment of 433 primary events in the study should occur quarterly by a telephone call: the final follow-up visit should be in-person, if at all possible, and should be performed within approximately 30 days after the attainment of 433 primary efficacy events in the study.

SAEs (that occurred within 30 days after the last study dose of double-blind study drug) and study outcomes will be documented at all follow-up contacts.

There are three study periods expected to last up to of 60 months in duration:

(1) a screening period of up to 14 days, (2) a treatment period lasting until the earlier of a subject's treatment

[name]

12

discontinuation and the attainment of 433 primary efficacy events and (3) a follow-up period lasting until the latter of 30 days after treatment discontinuation or the attainment of 433 primary efficacy events.

Expected duration of the study, from first subject first visit through last subject, last visit is approximately 60 months.

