8.2 Endpoints Definitions

8.2.1 Safety Endpoints

- Primary Safety Endpoint

The primary safety endpoint will be time to first occurrence of confirmed major bleeding.

- Secondary Safety Endpoints

The secondary safety outcome for this trial is a composite of confirmed major bleeding and confirmed clinically significant non-major bleeding. Other safety outcome measures will also be assessed, and will include minor bleeds, fractures and other AEs as well as abnormal standard clinical laboratory test results. All major bleeding and clinically relevant non-major bleeding outcomes will be adjudicated by the CEC.

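### The secondary safety composite (major or clinically relevant non-major bleeding) has no analysis of its own in the protocol; only separate category incidences, with no person-time denominator, are specified over a treatment period that can differ by arm

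*Protocol*

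**What the plan says.** **Endpoint.** The Synopsis (Criteria for Evaluation) states: "The secondary safety outcome for this trial is a composite of confirmed major bleeding and confirmed clinically relevant non-major bleeding". Section 8.2.1 names the same composite with a different adjective: "composite of confirmed major bleeding and confirmed clinically significant non-major bleeding". Neither place defines it as a time to first event.

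**Analysis.** Under Secondary Safety Analysis, section 8.3.2 begins "The incidence of confirmed major bleeding events, confirmed clinically relevant non-major bleeding events" and ends "minor bleeding events and all bleeding AEs occurring through the end of the treatment period will be summarized by treatment group". The Synopsis (Safety Analysis) carries the same sentence. The composite is in neither list.

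**Window.** Section 4.1 describes "a treatment period lasting until the earlier of a subject's treatment" discontinuation and the attainment of 433 primary efficacy events; section 6.1 gives the same rule.

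**Contrast.** The paragraph just above in 8.3.2 deals with major bleeding: "The primary safety endpoint will be time to first occurrence of major bleeding during the treatment period". It specifies a relative risk with two-sided 95% CI, a p-value, a Cox model stratified by prior warfarin status, Kaplan-Meier estimates, and censoring of subjects without events.

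**The concern.** Two things follow from setting the endpoint beside its analysis.

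First, the section headed for the secondary safety analysis does not contain the secondary safety endpoint. If it is followed literally, the composite is never estimated. Readers cannot rebuild it from the listed parts, because a subject may have both a CRNM and a major bleed and would be counted in each category.

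Second, the summaries run over time on drug, and that time is set by each subject's own discontinuation. A proportion of randomised subjects with an on-drug bleed depends on the bleeding hazard and also on how long subjects stay on drug. If one arm stops sooner, it has less time in which to bleed and looks safer even when the hazards are equal. The authors guarded against this for major bleeding but wrote no equivalent for the composite or for CRNM bleeding.

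At stake is the comparison on the second-ranked bleeding endpoint. The major-bleeding result and the testing hierarchy are not at stake.

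**Working it through.** The protocol gives no figure for this endpoint, so there is none to reproduce.

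**Step 1. Endpoint against analysis**

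| | Named as endpoint | Analysis specified |
|---|---|---|
| Major bleeding | Primary safety (Synopsis, 8.2.1) | Cox, RR with 95% CI, p-value, Kaplan-Meier, censoring |
| Major or CRNM bleeding | Secondary safety (Synopsis, 8.2.1) | None listed |
| CRNM alone, minor, all bleeding AEs | Not as the secondary composite | Incidence by arm through the end of treatment |

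**Step 2. The parts do not give the composite.** P(major or CRNM) = P(major) + P(CRNM) − P(both). The last term is not among the planned summaries.

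**Step 3. Size of the distortion if the incidence is a simple proportion**

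Inputs from the protocol: 7,843 subjects per arm; average follow-up 2.3 years (Synopsis), used here as a common follow-up T.

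Assumed, because the protocol gives no values: a constant bleeding hazard h, the same in both arms, at 3, 6 or 10 per 100 patient-years (PY); a constant discontinuation hazard d of 10 per 100 PY in one arm and 10, 12, 14 or 20 in the other; discontinuation unrelated to bleeding risk.

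Expected proportion with a first bleed on drug:

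p = h/(h+d) × [1 − exp(−(h+d)T)]

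At h = 0.06:

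- d = 0.10: 0.06/0.16 × (1 − e^−0.368) = 11.55%
- d = 0.12: 0.06/0.18 × (1 − e^−0.414) = 11.30%
- d = 0.14: 0.06/0.20 × (1 − e^−0.460) = 11.06%
- d = 0.20: 0.06/0.26 × (1 − e^−0.598) = 10.39%

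Ratios to the d = 0.10 arm, where the true hazard ratio is 1.00:

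| Discontinuation per 100 PY | Ratio (earlier-stopping arm / other) | Inverse | 95% CI at 6/100 PY |
|---|---|---|---|
| 10 vs 10 | 1.00 | 1.00 | 0.92 to 1.09 |
| 10 vs 12 | 0.98 | 1.02 | 0.90 to 1.07 |
| 10 vs 14 | 0.96 | 1.04 | 0.88 to 1.05 |
| 10 vs 20 | 0.90 | 1.11 | 0.82 to 0.98 |

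The CI uses SE(log ratio) = √[(1−p₁)/(n p₁) + (1−p₂)/(n p₂)] with n = 7,843. The ratios barely change for h of 3 or 10 per 100 PY.

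**Step 4. How often such a CI would exclude 1 although the hazards are equal** (for h = 3, 6, 10 per 100 PY):

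- 10 vs 12: about 6%, 8%, 10%
- 10 vs 14: about 10%, 16%, 24%
- 10 vs 20: about 37%, 64%, 85%

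The nominal figure is 5%. These percentages apply only if someone forms a ratio and CI from the proportions; the protocol does not say that anyone will.

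**Step 5. A person-time analysis under the same assumptions.** Mean time at risk is [1 − exp(−(h+d)T)]/(h+d). At h = 0.06 it is 1.92 years for d = 0.10 and 1.73 years for d = 0.20. Dividing the proportions by these times gives 0.1155/1.924 = 0.060 and 0.1039/1.731 = 0.060, which recovers equal rates.

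**The case against.** The strongest reply is that this belongs in the SAP. The model, interval and denominator for a secondary safety composite outside the testing hierarchy are commonly left there, and nothing in 8.3.2 says the composite will not be analysed. That stands against any claim that the composite will never be compared; the documents show only that the protocol specifies no comparison. It does not remove the mismatch, because the protocol is not silent: it has a section for this analysis, and that section omits the endpoint.

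Next, the word incidence does not exclude a rate per patient-year, and the secondary endpoint is not defined as time to event. Both points are fair. A descriptive summary does not contradict the endpoint definition, and the distortion in the working arises only if a proportion is meant. No denominator is stated, however, and the contrast with the preceding paragraph leaves the text at best ambiguous.

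A reader might also infer that the main bleeding harm could be misreported. The documents do not support this. Major bleeding is the primary safety endpoint, has a censored time-to-event analysis, and enters the hierarchical procedure.

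Finally, a reader might take the 10 versus 20 case as a forecast of a spurious 10% reduction. It is the extreme of an assumed range. Nothing in the protocol says that discontinuation will differ by arm, or in which direction.

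**Conclusion.** The point holds in limited form. The named secondary safety composite has no matching analysis in the Synopsis or 8.3.2, and the category summaries given instead carry no person-time denominator over a window that each subject's discontinuation can cut short.

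The effect is confined to the composite and to CRNM bleeding. Read as a proportion, the arm ratio would be off by about 2% to 4% for modest differences in discontinuation and about 10% if discontinuation doubled. It would be undistorted if discontinuation were equal, and the sign depends on which arm stops sooner. These sizes rest on assumed constant hazards, discontinuation unrelated to bleeding, and 2.3 years of follow-up for all subjects. The mismatch between endpoint and analysis rests on the text alone and needs none of these assumptions.

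This is a cheap improvement worth making. It does not threaten the primary safety conclusion.

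**What to change.** - In 8.3.2 (Secondary Safety Analysis) and the Synopsis, add an analysis of time to first confirmed major or CRNM bleed during the treatment period. Use the Cox model already specified for the primary safety endpoint (treatment group, stratified by prior warfarin/VKA status), and report the hazard ratio, 95% CI and Kaplan-Meier estimates.
- Report each bleeding category per 100 patient-years of treatment alongside the counts.
- In 8.2.1, call the non-major component clinically relevant, as in the Synopsis, 6.2.1 and 8.3.2. The phrase clinically significant bleeding is used for other purposes in 5.5.2 (unblinding) and 6.2.1.1 (management of bleeding).

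The cost is wording and a few tables. Bleed onset date and time are recorded (6.2.1.1), both components are adjudicated (6.2.1, 8.2.1), and the treatment-period censoring is already needed for the primary safety analysis. The one small downside is an extra reported comparison, which sits outside the testing hierarchy and uses no alpha.
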